***At week 260 or end of study visit***

**Progression of Disease (PD)** will be defined as a  $\geq 25\%$  increase on the 12 month MRI in the sum of the product of the biperpendicular diameters of enhancing disease; or new lesions; or substantial worsened T2/FLAIR; or significant clinical neurological decline unexplained by a change in medication or concurrent comorbidities. The SPD is the sum of the products of biperpendicular diameters of the measurable enhancing lesions (max 5 lesions)

**Complete Response (CR)** will be defined as the disappearance on the month 12 MRI or CT scan of all enhancing disease, no new lesions, with stable or improved T2/FLAIR; no more than physiological steroids; clinically stable or improved

**Partial Response (PR)** will be defined as a  $\geq 50\%$  decrease on the month 12 MRI or CT scan in the sum of the products of the biperpendicular diameters of enhancing disease, no new lesions, stable or improved T2/FLAIR, stable ( $>2$  months) or decreased steroid dose, clinically stable or improved

**Stable Disease (SD)** will be defined as a patient who do not qualify for complete response, partial response, or progressive disease, stable or improved T2/FLAIR; stable ( $>2$  months) or decreased steroid dose, clinically stable or improved

**Overall survival (OS)** will be defined as the time from baseline to the date of death from any cause. Follow up times of patients who are lost to follow up will be recorded and censored. The censoring time point (date last known to be alive) will be recorded.

**Objective Response Rate (ORR)** will be defined as the number of patients with CR + PR - divided by the total number of patients at time points 12, and every 12 months thereafter.

**Progression Free Survival (PFS)** will be defined as the time from baseline to documented PD or death from any cause. Patients without event would be censored at the last valid tumor assessment (before starting new anti-cancer therapy) at which they were known to be progression-free.

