1. STATISTICAL STATEMENT AND ANALYTICAL PLAN

1.1. Sample Size Considerations

A convenience sample of thirty (30) patients is based on recruitment feasibility. This sample size will permit estimation of dichotomous outcome rates with margins of error of less than 18% (based on a significance level of 0.05) and estimation of continuous parameter means to within 0.36 standard deviations. This is an early stage study, so analysis will focus on descriptive statistics. Continuous parameters will be summarized by means and 95% confidence intervals or by medians and interquartile ranges, as appropriate. Dichotomous outcomes will be summarized with point estimates of the rate, as well as 95% confidence intervals. Time-to-event data will be summarized using Kaplan-Meier curves.

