1.3.2. Secondary Endpoints

Based on the results of Stupp *et al* (2005) (3), if avelumab had no effect then we would expect to see one-year overall survival and progression-free survival rates of 60% and 27%, respectively. We will conclude that we have preliminary evidence of benefit if either of our observed rates is significantly better based on a one-sided t-test at the 0.2 level of significance. With our projected sample of 30, this corresponds to concluding benefit if at least 21 patients survive to one-year or if at least 11 have survived without progression of disease.

Radiological tumor response will be graded according to the immunotherapy Response Assessment for Neuro-Oncology (iRANO)

Progression of Disease (PD) will be defined as a $\geq 25\%$ increase on the 12 month MRI or CT scan in the sum of the product of the biperpendicular diameters of enhancing disease; or new lesions; or substantial worsened T2/FLAIR; or significant clinical neurological decline unexplained by a change in medication or concurrent comorbidities. The SPD is the sum of the products of biperpendicular diameters of the measurable enhancing lesions (max 5 lesions).

Complete Response (CR) will be defined as the disappearance on the month 12 MRI or CT scan of all enhancing disease, no new lesions, with stable or improved T2/FLAIR; no more than physiological steroids; clinically stable or improved

Partial Response (PR) will be defined as a $\geq 50\%$ decrease on the month 12 MRI or CT scan in the sum of the product of the biperpendicular diameters of enhancing disease, no new lesions, stable or improved T2/FLAIR, stable (>2 months) or decreased steroid dose, clinically stable or improved

Stable Disease (SD) will be defined at 12 months when a patient do not qualify for complete response, partial response, or progressive disease, stable or improved T2/FLAIR; stable (>2 months) or decreased steroid dose, clinically stable or improved

Overall survival (OS) will be defined as the time from baseline to the date of death from any cause.

Objective Response Rate (ORR) will be defined the number of patients with either CR or PR divided by the total number of patients.

Progression Free Survival (PFS) will be defined as the time from baseline to documented PD or death from any cause.

Results will be stratified according to MGMT status, baseline age (>50 yrs), baseline Karnofsky performance score (score of 100), radical tumor resection vs biopsy, primary versus secondary GBM,

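### The one-year benefit rule rests on a t-test of a yes/no outcome, with cut-offs worked out only for 30 patients of known one-year status; the plan gives no rule for another n or for censored patients

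*SAP*

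**What the plan says.** SAP 1.3.2, repeated in protocol 12.3.2, sets reference one-year rates of 60% for OS and 27% for PFS. Benefit is concluded if either observed rate is "significantly better based on a one-sided t-test at the 0.2 level of significance". The text then gives counts: "With our projected sample of 30, this corresponds to concluding benefit if at least 21 patients survive to one-year", or if at least 11 are alive without progression.

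Protocol 5.2 defines both outcomes as times from baseline and censors them. OS patients lost to follow-up are censored when last known alive. For PFS, "Patients without event would be censored at the last valid tumor assessment (before starting new anti-cancer therapy") at which they were known to be progression-free. The SAP's own OS and PFS definitions carry no censoring rule. SAP 1.1 adds: "Time-to-event data will be summarized using Kaplan-Meier curves". That summary is not linked to the benefit rule.

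Neither document says how a patient censored before one year enters the count, or which cut-offs apply if the number evaluable is not 30.

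**The concern.** This is the only efficacy decision rule in the plan. It names a test made for continuous means, applies it to a proportion, and states the result for one case only. The sample of 30 is a convenience sample, and the protocol itself provides for censoring, so another case is quite possible.

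Two readings are then open, and each has its own cost:

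- The t-test is the rule and is redone at the actual n. Its true error may then exceed the stated level.
- The counts 21 and 11 are the rule. The handling of censored patients then decides how strict it is.

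In an open-label, single-center trial, leaving that choice until the data are known weakens any statement of preliminary benefit.

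**Working it through.** **Inputs.** Null rates 0.60 (OS) and 0.27 (PFS), one-sided level 0.2, n = 30, cut-offs 21 and 11, benefit if either passes: all from SAP 1.3.2. No alternative rates or dropout rate are given. True rates of 70% and 40% and losses of 5% and 10% are assumptions.

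**1. The plan's own cut-offs.** For 0/1 data, t = (p̂ − p0) / √[p̂(1 − p̂)/(n − 1)] on n − 1 degrees of freedom. The exact p-value is P(X ≥ k) for X ~ Bin(n, p0).

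| Result | t | t-test p | exact p |
|---|---|---|---|
| OS 20/30 | 0.0667/√(0.2222/29) = 0.762 | 0.226 | 0.291 |
| OS 21/30 | 0.10/√(0.21/29) = 1.175 | 0.125 | 0.176 |
| PFS 10/30 | 0.0633/√(0.2222/29) = 0.723 | 0.238 | 0.276 |
| PFS 11/30 | 0.0967/√(0.2322/29) = 1.080 | 0.144 | 0.161 |

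Both tests give 21 and 11, so the plan's figures are reproduced. The t-test p-value is still smaller than the exact one (0.125 against 0.176 for OS).

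**2. Reading A: t-test redone at the actual n.** Find the smallest k with t-test p ≤ 0.2, then its true level P(X ≥ k) under the null.

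| n | OS t-test cut-off (true level) | OS exact cut-off | PFS t-test cut-off (true level) | PFS exact cut-off |
|---|---|---|---|---|
| 24 | 17 (0.192) | 17 | 9 (0.175) | 9 |
| 25 | 18 (0.154) | 18 | 9 (0.211) | 10 |
| 26 | 18 (0.226) | 19 | 10 (0.138) | 10 |
| 27 | 19 (0.184) | 19 | 10 (0.168) | 10 |
| 28 | 19 (0.259) | 20 | 10 (0.201) | 11 |
| 29 | 20 (0.215) | 21 | 11 (0.133) | 11 |
| 30 | 21 (0.176) | 21 | 11 (0.161) | 11 |
| 31 | 21 (0.245) | 22 | 11 (0.192) | 11 |
| 32 | 22 (0.205) | 23 | 11 (0.225) | 12 |
| 33 | 23 (0.169) | 23 | 12 (0.155) | 12 |

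The level is breached at several sizes. It holds on both endpoints at 24, 27, 30 and 33.

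**3. Reading B: 21 and 11 stay fixed.** True level (OS, PFS) by number evaluable:

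- n = 27: 0.042, 0.086
- n = 28: 0.074, 0.108
- n = 29: 0.119, 0.133
- n = 30: 0.176, 0.161
- n = 31: 0.245, 0.192
- n = 32: 0.323, 0.225

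Up to 30 the rule only becomes stricter. It exceeds 0.2 for OS from n = 31 and for PFS from n = 32.

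The cost below 30 is power. If a fraction L of patients is lost by one year, independently of outcome, and lost patients are not successes, each of the 30 succeeds with probability p(1 − L):

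- OS, true 70%: P(Bin(30, 0.70) ≥ 21) = 0.59. At 5% loss, p = 0.665 gives 0.42. At 10%, p = 0.63 gives 0.28.
- PFS, true 40%: P(Bin(30, 0.40) ≥ 11) = 0.71. At 10% loss, p = 0.36 gives 0.54.

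Handling also moves the error. Suppose 2 of 30 are lost. Counted as failures, the errors are 0.074 (OS) and 0.108 (PFS). Counted as successes, they are P(Bin(28, 0.60) ≥ 19) = 0.259 and P(Bin(28, 0.27) ≥ 9) = 0.335.

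**4. Kaplan-Meier alternative.** The lower log-log bound is S^exp(z·se/|ln S|), with z = 0.8416 and se² = Σ d/[r(r − d)], where d is deaths (or PFS events) and r the number at risk. With complete data, se² = (1 − S)/(nS).

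- OS 21/30: se = √(0.3/21) = 0.1195, and the bound is 0.7^1.326 = 0.623, above 0.60. OS 20/30 gives 0.589.
- PFS 11/30 gives 0.293, above 0.27. PFS 10/30 gives 0.262.

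So 21 and 11 are kept. In simulation at n = 30 with exponential event times and 10% random loss, power is about 0.60 (OS) and 0.73 (PFS), at level 0.19 to 0.20.

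**5. Either endpoint.** A patient alive without progression is also alive, so under the null the categories are 0.27 (progression-free), 0.33 (alive after progression) and 0.40 (dead). The trinomial probability of at least 11 in the first category, or at least 21 in the first two, is 0.269 for n = 30. Independence would give 1 − (1 − 0.176)(1 − 0.161) = 0.309. The upper bound is 0.176 + 0.161 = 0.338 (unrounded inputs).

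**The case against.** The case for leaving the rule alone has several sound parts.

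- At the planned 30 the test label changes nothing, because the exact test gives the same cut-offs.
- The counts are introduced as what the test means at a projected 30, so they can be read as an illustration. Nothing in the plan foresees more than 30 patients.
- Loss may be small. Protocol 9.3.7 requires survival calls every 4 weeks, allows public sources for survival status, and continues disease assessments after early withdrawal. The synopsis and protocol 8.2 treat bevacizumab or re-irradiation as progression, which narrows PFS censoring.
- The rule is secondary, in a safety study whose SAP says analysis will be mainly descriptive.
- The log-log bound is itself approximate. With complete data its level is 0.237 for PFS at n = 29 and 0.245 for OS at n = 31.

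All of this stands, and it limits the point. It does not supply the missing rule. If the counts are an illustration, the t-test is operative, and its level is breached at several sizes.

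A reader might infer that the 0.2 level holds only with exactly 30 patients. The figures do not support that: fixed counts stay below 0.2 for every n up to 30, and the redone t-test also holds at 24, 27 and 33. A reader might also infer that the plan counts censored patients as failures. The text defines no denominator and is silent on this; failure is only one possible handling. Finally, the level breaches and the power loss belong to different readings and should not be added together.

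**Conclusion.** The point holds in a limited form. Per endpoint, the rule is sound when about 30 patients all have known one-year status. Outside that case the plan is incomplete, and the consequence depends on the reading: a true level of up to 0.259 for OS and 0.225 for PFS at n = 24 to 33 if the t-test is redone, or a stricter rule with lower power if the counts are kept and censored patients are not successes. The power figures rest on assumed true rates and on an assumed random loss, which may be too high for OS.

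Separately, the stated 0.2 applies to each endpoint. The conclusion of benefit from either one carries about 0.27 with 30 complete patients, under the null rates with nested endpoints. This should be corrected before analysis, but it does not touch the primary safety objective.

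**What to change.** In SAP 1.3.2 and protocol 12.3.2:

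1. Replace the t-test. If every patient has known one-year status, use the exact binomial test at one-sided 0.2 and the actual n. Cut-offs (OS/PFS): 28 patients, 20/11; 29, 21/11; 30, 21/11; 31, 22/11.
2. If any patient is censored before one year on an endpoint, conclude benefit on that endpoint when the one-sided 80% lower log-log (Greenwood) bound of the one-year Kaplan-Meier estimate exceeds 60% (OS) or 27% (PFS). State that this level is approximate.
3. Present 21 and 11 as the cut-offs for 30 complete patients only.
4. Carry the censoring rules of protocol 5.2 into the SAP.
5. State that, because either endpoint suffices, the overall false-positive risk with 30 complete patients is about 0.27.

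The cost is wording in two documents. No extra patients, visits or data are needed, Kaplan-Meier estimation is already planned, and the cut-offs at 30 complete patients do not change.

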### **Secondary:**

Radiological tumor response will be graded according to the Immunotherapy Response Assessment for Neuro-Oncology (iRANO) criteria by a single study radiologist based on the gadolinium enhanced brain MRI or CT scan performed at the study center at baseline and Q52 weeks or within 2 weeks of the end of study visit and the evaluations of locally obtained MRI's or CT scan.

Clinical tumor response as per the iRANO criteria will be evaluated by the principal investigator based on the protocol specified neurological exams

The OS and PFS will be stratified according to MGMT status, baseline age (>50yrs), baseline Karnofsky performance score (score of 100), whether the patient had a radical tumor resection vs biopsy and according to histopathological diagnosis of primary versus secondary GBM

Changes in the daily corticosteroid dose will be discouraged during the 2 week period prior to the week 52 or end of study MRI or CT scan.

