### **5.2. Secondary**

Radiological tumor response will be graded according to the Immunotherapy Response Assessment for Neuro-Oncology (iRANO) criteria by a single study radiologist based on the gadolinium enhanced brain MRI or CT scan performed at the study center at baseline and Q52weeks or within 2 weeks of an end of study visit and evaluations of locally obtained MRI's or CT scan.

Clinical tumor response as per the iRANO criteria will be evaluated by the principal investigator based on the protocol specified neurological exams

The iRANO endpoints will be stratified in relation to MGMT status, baseline age (>50yrs), baseline Karnofsky performance score (score of 100), radical tumor resection vs biopsy, primary versus secondary GBM.

Changes in the daily corticosteroid dose will be discouraged during the 2 weeks period prior to the week 52 or end of study visit MRI or CT scan.

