**Progression of Disease (PD) based on radiographic parameters:**

Patients with stable clinical neurological status with stable dexamethasone dose of 12mg/day or less and evidence of radiological progression defined as a  $\geq 25\%$  increase in the sum of the biperpendicular diameters of enhancing disease; or substantial worsened T2/FLAIR; or new lesions on gadolinium enhanced MRI or CT scan done less than 6 months from baseline will require confirmation on a repeat imaging done 3 months later. The first MRI or CT scan showing progression will act as the new baseline and if progression is confirmed the date of progression will be backdated to the new baseline MRI or CT scan where the progression was first noted.

If the first radiological evidence of progression or new lesions occurs 6 months or more from baseline then no confirmatory imaging will be required.

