### **12.3.2. Secondary Endpoints**

Based on the results of Stupp *et al* (2005) (3), if avelumab had no effect then we would expect to see one-year overall survival and progression-free survival rates of 60% and 27%, respectively. We will conclude that we have preliminary evidence of benefit if either of our observed rates is significantly better based on a one-sided t-test at the 0.2 level of significance. With our projected sample of 30, this corresponds to concluding benefit if at least 21 patients survive to one-year or if at least 11 have survived without progression of disease.

Radiological tumor response will be graded according to the immunotherapy Response Assessment for Neuro-Oncology (iRANO)

**Progression of Disease (PD)** will be defined as a  $\geq 25\%$  increase on the 12 month MRI or CT scan in the sum of the product of the biperpendicular diameters of enhancing disease; or new lesions; or substantial worsened T2/FLAIR; or significant clinical neurological decline unexplained by a change in medication or concurrent comorbidities. The SPD is the sum of the products of biperpendicular diameters of the measurable enhancing lesions (max 5 lesions).

**Complete Response (CR)** will be defined as the disappearance on the month 12 MRI or CT scan of all enhancing disease, no new lesions, with stable or improved T2/FLAIR; no more than physiological steroids; clinically stable or improved

**Partial Response (PR)** will be defined as a  $\geq 50\%$  decrease on the month 12 MRI or CT scan in the sum of the product of the biperpendicular diameters of enhancing disease, no new lesions, stable or improved T2/FLAIR, stable ( $>2$  months) or decreased steroid dose, clinically stable or improved

**Stable Disease (SD)** will be defined at 12 months when a patient do not qualify for complete response, partial response, or progressive disease, stable or improved T2/FLAIR; stable ( $>2$  months) or decreased steroid dose, clinically stable or improved

**Overall survival (OS)** will be defined as the time from baseline to the date of death from any cause.

**Objective Response Rate (ORR)** will be defined the number of patients with either CR or PR divided by the total number of patients.

**Progression Free Survival (PFS)** will be defined as the time from baseline to documented PD or death from any cause.

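### SAP 1.3.2 and protocol 12.3.2 tie size-based progression to the 12-month scan and do not apply protocol 5.2's confirmation, dating and censoring rules to PFS

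*SAP*

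**What the plan says.** SAP 1.3.2 and protocol 12.3.2 carry the same text. Progression by size is a 25% or greater "increase on the 12 month MRI or CT scan in the sum of the product of the biperpendicular diameters of enhancing disease". New lesions, worsened T2/FLAIR and clinical decline are listed as alternatives. PFS "will be defined as the time from baseline to documented PD or death from any cause". Benefit is concluded if at least 11 of 30 are alive and progression-free at one year, or if at least 21 survive.

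Protocol 5.2 has a fuller scheme under its iRANO heading, in two parts.

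- **During the study.** Radiographic progression by size, T2/FLAIR or new lesion on a scan before month 6 needs a repeat scan 3 months later. The scan that first shows it becomes the new reference, and once the repeat scan bears it out, "the date of progression will be backdated to the new baseline MRI or CT scan where the progression was first noted". A different rule holds from month 6 on: "If the first radiological evidence of progression or new lesions occurs 6 months or more from baseline then no confirmatory imaging will be required".
- **Week 260 or end-of-study visit.** The 12-month definitions stand here, followed by a PFS definition that censors patients without an event at the last valid tumour assessment before new anti-cancer therapy.

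Study-specified scans are at baseline and every 52 weeks. Local scans are taken about every 3 to 4 months (Synopsis, Radiological assessment). Protocol 5.2 includes "evaluations of locally obtained MRI's or CT scan" in grading, and 9.3.5 uses local scans after month 6 to ascertain progression. Protocol 9.3.5 also compares the 12-month scan with baseline.

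**The concern.** The sections that govern the analysis keep only the visit-based definition. They drop the during-study rule, the two sub-headings that separate event dating from response at a visit, and the censoring rule. A statistician who follows SAP 1.3.2 literally would ignore size-only growth until the 12-month scan. The same statistician would accept an unconfirmed early new lesion that protocol 5.2 would not.

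Both the planned Kaplan-Meier curve (SAP 1.1) and one-year PFS status depend on this. One-year PFS is one of two routes to declaring preliminary evidence of benefit, and in a sample of 30 the rule can turn on one patient.

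**Working it through.** **1. The plan's own threshold.** Inputs from SAP 1.3.2: n = 30, null one-year PFS 27%, one-sided level 0.2. With X binomial(30, 0.27), the expected count is 30 × 0.27 = 8.1, P(X ≥ 11) = 0.161 and P(X ≥ 10) = 0.276. The one-sample t-test that the plan names gives 0.145 for 11 and 0.238 for 10. So 11 is the smallest significant count, and the stated rule reproduces.

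**2. The two rules side by side.**

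| Event | SAP 1.3.2 / protocol 12.3.2 as written | Protocol 5.2 |
|---|---|---|
| Size growth of 25% or more first seen before month 6 | Not progression until the 12-month scan | Progression if confirmed 3 months later, dated at the first scan |
| Same, first seen from month 6 | Not progression until the 12-month scan | Progression at that scan |
| New lesion or T2/FLAIR worsening before month 6 | Progression, no confirmation asked | Progression only if confirmed, then backdated |
| No event | No censoring rule | Censored at last valid assessment |

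The third row takes the 12-month time point as attached to the size criterion only, which is how the sentence is built.

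**3. Dating.** Delay = 12 − month of the first progressing scan.

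- No confirmation needed: month 6 gives 6, month 8 gives 4, month 9 gives 3.
- Only if confirmed 3 months later: month 3 gives 9, month 4 gives 8. Without confirmation, 5.2 gives no progression date there.

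**4. Status (hypothetical patient).** The sum of products of diameters (SPD) is 100 at baseline, 130 at month 8 and 110 at month 12. At month 8, 130/100 = +30%, which is progression under 5.2. At month 12, 110/100 = +10%, which is not progression under the SAP.

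**5. Reference scan (hypothetical patient).** SPD is 100 at baseline, 130 at month 4, 135 at month 7 and 140 at month 12. Protocol 5.2 does not say what confirms an early progression.

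- If confirmation needs a further 25% over the new baseline, 135/130 = +3.8% does not confirm. The month-12 scan is then +40% against baseline (140/100, as in 9.3.5) but +7.7% against the new baseline (140/130).
- If persistence over the original baseline is enough, 135/100 = +35% confirms, progression is dated at month 4, and the conflict at month 12 does not arise.

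**6. Effect on the 11-of-30 rule.**

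- One patient moved to progression-free matters when the count is otherwise 10: P(X = 10) = 0.2755 − 0.1613 = 0.114 at 27%. At true rates of 30%, 35% and 40% it is 0.142, 0.150 and 0.115.
- Assumed shift of one patient in 30 to progression-free: with p = 0.27 + 1/30, P(X ≥ 11) = 0.283. Moving the count by a fixed 1 gives P(X ≥ 10) = 0.276. Either way it is about 0.28, against 0.16.
- Assumed shift of one the other way: with p = 0.27 − 1/30, P(X ≥ 11) = 0.077. The fixed shift gives 0.084. Either way it is about 0.08.

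**The case against.** The strongest reply is that the rule exists and is prespecified. Protocol 5.2 separates during-study progression from visit categories, 9.3.5 says local scans are used, and both analysis sections name iRANO. The SAP is close to a copy of protocol section 12 and does not claim to replace section 5. That stands in part: a reader might infer that the dating rule is left open until data are seen, and the documents do not support so strong a statement. But the iRANO sentence concerns grading of tumour response and cites no section, and an explicit definition that differs from 5.2 follows it. The analysis sections therefore state a conflicting rule, which goes beyond a missing cross-reference.

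A second reply is that growth which persists still fails at week 52, so status often agrees. True. Bevacizumab and re-irradiation, two routes to later shrinkage, already count as evidence of progression (Synopsis; 8.2). Other routes remain: avelumab combined with other therapies after confirmed progression (4.2), second resections, and the stabilisation or regression after radiological progression that the exploratory analyses set out to describe. The end-of-treatment study scan is also discretionary after avelumab-related adverse events or clinical progression (9.3.4).

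A reader might also infer that the literal reading inflates PFS, or that only size-based progression is affected. Neither follows. The early new-lesion and T2/FLAIR cases go the other way, and so may the SAP's clinical criterion, which has no ECOG cut-off or duration. Finally, PFS is secondary, the study is mainly descriptive with a safety primary objective, and OS is untouched. That limits the weight of the point.

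**Conclusion.** The point holds. The analysis sections state a progression rule that conflicts with protocol 5.2 for events before month 12, and they omit its censoring rule. Followed as written, they misdate some PFS events by 3 to 6 months, or by 8 to 9 months for confirmed early progression, and can change one-year status in either direction.

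The delays assume local scans on schedule every 3 or 4 months. The tail probabilities of about 0.28 and 0.08 rest on assumed one-patient shifts, because the documents give no frequency of affected patients. The net direction is not established. The reference-scan conflict is conditional on what counts as confirmation, which the protocol text leaves unstated; the Appendix 1 algorithm is a figure not available here. The point should be fixed before analysis, but it does not undermine the primary safety objective or OS.

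**What to change.** In SAP 1.3.2 and protocol 12.3.2, state that:

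1. Radiographic progression for PFS is confirmed and dated by the protocol 5.2 during-study rules on any study or local scan, using the sum of products of diameters. The 5.2 wording, "increase in the sum of the biperpendicular diameters of enhancing disease", omits the product. PFS ends at the earliest of radiographic progression, clinical progression, any other event the protocol counts as progression, or death.
2. The month-12 definitions classify response at that visit only. A patient with an earlier dated progression is not progression-free at one year.
3. The 5.2 censoring rule applies to PFS, with a stated rule for how a patient censored before one year counts toward the 11 of 30.
4. Before analysis, the sponsor reconciles the new baseline in 5.2 with the baseline comparison in 9.3.5 and says what confirms an early progression.

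Two sets of passages feed item 1 and must be reconciled by the sponsor before analysis. The clinical progression wording differs between 5.2, 8.4, 9.3.5 and SAP 1.3.2. Bevacizumab or re-irradiation is evidence of progression in the Synopsis and 8.2 but of a termination event in 4.2; both can hold, but the wording is uneven. No view is given here on which clinical rule is right; the point concerns dating PFS, not stopping treatment.

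The cost is wording plus SPD readings on local scans, copies of which are already obtained (9.3.5). Only study scans follow the predefined acquisition protocol, so local readings will be noisier, and PFS may come out slightly lower.
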